3. STUDY DESIGN

This is a randomized, blinded, placebo-controlled, cross-over study designed to treat CP in pediatric subjects with an IV infusion of autologous bone marrow mononuclear cells or autologous umbilical cord blood cells. A total of 30 subjects (15/arm) will be enrolled into the study. Subjects will be randomized 2:1 (treatment: sham). All subjects will return for follow-up at 6 months, 12 months, and 24 months post-treatment. At the 12 months post-treatment visit, those subjects who originally received the sham will be offered the BMMNC or hUCB treatment (Figure 1).

Figure 1.

Thirty subjects will provide a preliminary assessment of potential SAEs with a 10 to 15% incidence that we would be able to detect with reasonable confidence. The sample size would also allow us to acquire point estimates of different events that we would use for a larger efficacy study. The sample size determination is based on the historical treatment effect size of 15% decrease in gray and white matter volumes. Preservation

of this volume is based on the Phase 1 pediatric acute treatment of severe TBI using autologous bone marrow derived mononuclear cells as compared to historical control volumetric analyses by Wilde et al. (Wilde, E, et. al. 2005; Cox, C et al., 2011.)

Drug/Biologic: A single dose of intravenously administered autologous BMMNC or hUCB. The BMMNC dose will be 6X10⁶ cells/kg body weight infused over 15 minutes at a 1 million cells/ml concentration. For the hUCB arm, the minimum acceptable dose will be 2X10⁶cells/kg body weight based on rodent data (Lu, 2001), and the maximum allowable dose will be 10X10⁶cells/kg. The target dose will be the maximum available dose within this range. The bone marrow harvest, the hUCB reanimation, cell processing and product infusion will occur at Children's Memorial Hermann Hospital and the Griffin Stem Cell Laboratory.

Placebo: 0.9% saline will be infused in an identical syringe over the same rate as if receiving a cell infusion, (See "Blinding of Placebo Infusion").

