4. SELECTION AND ENROLLMENT OF SUBJECTS

4.1 Inclusion Criteria

- 1. Children with diagnosis of Cerebral Palsy (spastic CP due to periventricular white matter damage or neonatal brain injury from perinatal stroke or intraventricular hemorrhage)
- 2. Gross Motor Function Classification Score level II-V
- 3. Ages 24 months to 10 years
- 4. English speaking, if verbal
- 5. Ability to travel to Houston for treatment and follow-up

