[figure not shown]
[figure not shown]

Figure 9: Reconstruction of right cst using FSL's probabilistictractography methodology (red/yellow probability map) overlaid onto color-coded reconstruction of diffusion tensors (red=interhemispheric; blue=superior-inferior; green=anterior-posterior).

Additionally, Freesurfer-generated volumetric measures from primary motor cortex and DTI measures of FA and MD from the corticospinal tract (CST) will be related to neurobehavioral assessments of function and outcome.

To study language networks, Freesurfer-generated volumetric measures from inferior frontal regions (e.g. pars opercularis and pars triangularis in yellow), temporal regions (superior- and middle-temporal not shown), and parietal regions (e.g. supramarginal and angular in green) will be related to language measures. Furthermore, DTI measures of FA and MD from the same GM regions and the AF/SL (in red) will be related to neurobehavioral assessments of function and outcome (Figure 10).

Figure 10

[figure not shown]

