9. STATISTICAL CONSIDERATIONS

9.1 Outcomes

9.1.1 Primary Safety Objective

Baseline characteristics of participants will be summarized using descriptive statistics and tabulations. Evaluation of data will be guided by exploratory analyses. All results will be reported as point estimates (percentages for binary outcomes and means \pm SD and median (range) for continuous outcomes) with corresponding interval estimates (two-sided 95% confidence intervals). No adjustments for multiple comparisons will be made and a p-value of 0.05 will be considered statistically significant.

These data are collected over time and will be longitudinal in nature with several predefined points of follow-up. We will use analytic strategies and methods applicable to such designs. For each participant in the cohort we have a set of "k" independent variables $\mathbf{x}' = (x_1, x_2, ..., x_k)$, of which some may be time varying (e.g., blood pressure) and others do not change over time (e.g., gender). In addition, the outcome variables of interest are also measured repeatedly over time (e.g., temperature, signs of infection, neurological exams, CBC, chem-20). We plan to explore any changes over time between hospital discharge and long-term follow-up at 6 months, 1 year, and 2 years after cell treatment with repeated measure model analyses. In this study, we plan to explore and identify potential factors associated with time to SAEs, AEs, death (refer to section 6.2), loss to follow-up (short term and long term), and improvements in functional outcomes (refer to section 6.3). We plan to explore the factors associated with the time to an event using survival analysis methods which incorporate information about the timing of withdrawals, deaths, and functional improvements (if any) of subjects during the follow up period. We plan to first use descriptive statistics to explore the characteristics of the subjects among events and then will use the Kaplan-Meier method to estimate the time to an event. Combined, these secondary analyses may provide useful preliminary estimates for the design of future cell studies.

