To examine brain-behavior relations (Efficacy Outcome Measure 2, section 1.2.2), we will first examine the distribution of variables to determine whether assumptions are met for Pearson or Spearman correlation approaches. To evaluate strength of brain-behavior relations, outcome scores will be correlated with specific macrostructural and microstructural metrics from the DTI. For global outcome, the GOS-EC score will be correlated with gray and white matter volumes and corpus callosum FA. For neurocognitive outcomes, the accompanying table shows the expected relations between outcomes and gray and white matter microstructural metrics. We expect positive correlation of dependent variables with FA and negative correlation of dependent variables with MD. Similar to our recent approach ([name] et al., 2012), brain-behavior analysis will also be completed using individual outcomes as dependent variables with group (Treatment, Control) and MRI/DTI variables as independent variables (e.g., examine the effect of group and FA of the corticospinal tract on fine motor scores; examine group and MD of dorsolateral frontal cortex on working memory scores).

Expected Relations of Neurocognitive Outcomes with Gray and White Matter						
Microstructure from Diffusion Tensor Imaging.						
Neurocognitive	Microstructure:	Microstructure:				
Outcome	Gray Matter MD	White Matter FA				
IQ		Corpus callosum				
Motor		Corticospinal				
GMFM-88						
Verbal Fluency		Arcuate/superior longitudinal				
PPVT4/EVT2		fasciculus				
Learning/Memory	Temporal cortex,					
NEPSY-II	hippocampus					

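### Section 9.1.2 specifies no age adjustment for the brain-behaviour analyses, so shared maturation alone could produce the expected positive correlation of corticospinal FA with GMFM-88

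*Combined protocol and SAP*

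**What the plan says.** Section 9.1.2 describes two brain-behaviour analyses.

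- **Correlation.** "To evaluate strength of brain-behavior relations, outcome scores will be correlated with specific macrostructural and microstructural metrics from the DTI". The choice of coefficient is left to the data: "we will first examine the distribution of variables to determine whether assumptions are met for Pearson or Spearman correlation approaches". No partial correlation is named, and the paragraph does not say which visit supplies the values.
- **Regression.** Models are fitted "using individual outcomes as dependent variables with group (Treatment, Control) and MRI/DTI variables as independent variables". One of the two worked examples is corticospinal FA with fine motor scores.

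The plan predicts that outcomes will correlate positively with FA. Its table pairs GMFM-88 with the corticospinal tract, and PPVT-4/EVT-2 with the arcuate/superior longitudinal fasciculus. NEPSY-II is paired with gray matter MD. IQ is paired with callosal FA but has no named test. Section 6.4.7 repeats the motor link: "DTI measures of FA and MD from the corticospinal tract (CST) will be related to neurobehavioral assessments of function and outcome".

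The entry criterion in section 4.1 is "Ages 24 months to 10 years". Appendix B lists GMFM-88 for every age band.

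Age does appear in section 9.1.2, but only in the model for Efficacy Outcome Measure 1 (imaging by group and time). A general clause allows covariates where needed; it is tied to comparability of the groups and gives socioeconomic status as its example. On significance, section 9.1.1 says: "No adjustments for multiple comparisons will be made and a p-value of 0.05 will be considered statistically significant".

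**The concern.** If two measures both rise with age, they correlate across a sample of mixed ages even when neither affects the other. The sponsor evidently expects the imaging metrics to depend on age, since Age is in the imaging model. FA is a raw metric. GMFM-88 is described in section 6.3.1 as an observation-based 88-item scale, with no standard score mentioned. The tests in sections 6.3.4 to 6.3.6, and VABS-2 in 6.3.3, are described as giving standard scores.

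The motor pair therefore has two sides that could both increase between ages 2 and 10. The direction would be the one that the plan predicts, so an artefact of maturation would look like confirmation. Section 1.2 gives the tract-to-motor relation a prominent place among the efficacy measures.

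**Working it through.** The documents give no power, sample size or expected correlation for this analysis, so there is no stated figure to reproduce.

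**Inputs from the documents**
- n = 30, from section 3: "A total of 30 subjects (15/arm) will be enrolled into the study". n = 15 is one cell-source arm.
- Allocation 2:1, from section 3.
- Significance level 0.05 without multiplicity adjustment, from section 9.1.1. Two-sided testing is assumed, in line with the two-sided intervals stated there.

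**Inputs that are assumptions**
- Correlation of age with FA, a, and of age with the score, b: each 0.3 to 0.7 for a score that is not age-normed; b = 0 for an age-normed score.
- Age uniform on 2 to 10 years, no link between FA and score other than age, and no treatment effect.

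**Step 1: critical correlation.** |r| = t / √(n − 2 + t²).
- n = 30: 2.048 / √(28 + 4.195) = 0.361.
- n = 15: 2.160 / √(13 + 4.667) = 0.514.

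**Step 2: correlation induced by age alone.** r = a × b.
- 0.3 × 0.3 = 0.09; 0.5 × 0.5 = 0.25; 0.6 × 0.6 = 0.36; 0.7 × 0.7 = 0.49.

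At n = 30 the value 0.36 already sits at the significance threshold.

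**Step 3: false-positive rates**, from 40,000 simulated trials per setting.

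| a = b | Raw r, n=30 | Group + FA model, n=30 | Age-partial r, n=30 | Raw r, n=15 | Age-partial r, n=15 |
|---|---|---|---|---|---|
| 0.3 | 7.4% | 7.4% | 5.0% | 6.2% | 5.1% |
| 0.5 | 26.5% | 25.9% | 5.2% | 14.2% | 5.1% |
| 0.6 | 52.1% | 50.5% | 4.9% | 26.5% | 5.0% |
| 0.7 | 83.1% | 81.6% | 5.0% | 49.0% | 4.9% |

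Adding group to the model gives almost no protection, because randomised group is unrelated to age on average.

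**Step 4: outcomes with age-normed scores.** With b = 0 and a = 0.5 or 0.7, the induced correlation is 0 and the unadjusted rate at n = 30 is 4.9%. If standard scores drifted down with age (b = −0.3, a = 0.7), the induced correlation is 0.7 × (−0.3) = −0.21. The two-sided rate is then 19.8%, but only 0.1% falls in the predicted positive direction.

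**The case against.** Several points on the other side have force.

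- **Most listed outcomes are not clearly exposed.** A reader might infer that maturation could generate all the predicted FA-function relations. The documents do not support that. PPVT-4 and EVT-2 are described as standard scores; NEPSY-II is too, and it is paired with MD. If these scores are age-normed and are the values analysed, Step 4 applies. This stands. GOS-EC, to be correlated with volumes and callosal FA, is not described in section 6.3, so its exposure cannot be judged.
- **A change-based analysis already exists.** Section 6.4.9 plans to compare the regions of interest with baseline and relate the changes to functional change. That would alter the bias. But 9.1.2 does not carry this analysis, and children of different ages may change at different rates, so age still matters.
- **The covariate clause might admit age.** It depends on group comparability. Perfectly balanced groups would not trigger it, yet the age confounding of a pooled correlation would remain.
- **The regressions follow a cited earlier approach.** Whether that approach adjusts for age cannot be checked from the documents. What can be said is that no age term is specified here.
- **The size is assumed.** Entry covers GMFCS II to V with varied lesions. Severity may dominate both FA and GMFM-88 and weaken their relations with age, and at 0.3 the inflation is slight. The return to 5% also follows by construction, since age was simulated as the only link.
- **Little depends on it.** A reader might infer that a spurious correlation would become the basis for powering later trials, or be taken as evidence that structural recovery drives function. The sentence in 6.4.9 about a structural metric for future studies follows the treated-versus-untreated comparison, which this confounding does not bias. No section states the causal reading.

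**Conclusion.** The point holds for a limited part of the plan. Section 9.1.2 specifies no age adjustment in the brain-behaviour correlations or in the group-plus-MRI models, and nothing elsewhere supplies one. The clearly exposed pair is GMFM-88 with corticospinal FA, and GOS-EC is a possible second.

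The inflation runs from about 7% to 83% at n = 30, and from about 6% to 49% at n = 15, as the assumed age correlations go from 0.3 to 0.7. With age partialled out it is about 5%. These figures rest on age correlations that the documents do not give and on age being the only link. They show what the unadjusted analysis permits, not what this trial will find.

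The randomised comparison, the primary safety outcome, the stopping rules and the sample size are unaffected. The analysis is secondary and exploratory, in a 30-child trial whose main purpose is safety.

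**What to change.** In section 9.1.2:

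1. Specify partial Pearson or Spearman correlations adjusted for age at the scan, and add age at assessment to the group-plus-MRI regressions. Do this at least for GMFM-88 and any other score that is not age-normed. Report unadjusted values alongside.
2. State for each outcome whether the raw or the standard score is analysed, and at which visit.
3. Carry the change-with-change correlation of section 6.4.9 into 9.1.2, adjusted for baseline age, so that the two sections describe the same analysis.

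Age is already needed for eligibility and for the imaging model, so no new data are required. The cost is one degree of freedom per analysis. At n = 30 the critical correlation moves from 0.361 to 2.052 / √(27 + 4.210) = 0.367. At n = 15 it moves from 0.514 to 2.179 / √(12 + 4.748) = 0.532.

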1.2 Secondary Objective

To determine if late functional outcomes are improved following the administration of autologous cells compared with subjects in the control group. Efficacy outcome measures:

- 1. aMRI volumetric white matter, grey matter, and CSF space volumes at Baseline, 1 year and 2 years post-treatment. Detailed volumetric analysis of the corpus callosum and white matter tract such as the corticospinal tract will be measured (fractional anisotropy and mean diffusivity) as well. Specific white matter tract analysis will be identified at baseline MRI and correlated with motor function studies as the primary lesion of interest. Total volumes and specific tract lesions will be analyzed and correlated with functional outcomes.
- 2. The following functional outcomes studies will be performed at baseline, 6 months, 1 year after infusion, and 2 year after infusion.
 - a. Gross Motor Function Measures
 - b. Psychological Assessment Batteries

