6.4.9 Secondary Imaging Outcome Measures & Correlation with Functional Outcome

As noted in the section, "CP Neuroimaging", cerebral palsy is a clinical diagnosis comprising a heterogeneous group of patients. This heterogeneity is manifest both in the dominant clinical symptom complex, but also in the imaging correlates of the symptoms. To that end, prior to treatment this study will quantify the degree of functional impairment (GFCMS level), and correlate it with the CP subtype and imaging abnormality. The imaging ROIs will be prospectively identified pre-treatment. Then, according to the qualitative and quantitative metrics, the imaging data will be recorded. Post-treatment, these same ROIs will be compared to the baseline data, and correlated with any changes in functional outcomes as measured by specific tasks on the GFCMS. Ultimately, the changes in WM and GM ROIs that are associated with CP will be compared with and without treatment using autologous bone marrow derived mononuclear cells or autologous cord blood mononuclear cells. These data will provide a structural metric around which future studies could be powered. Further, these data may provide potential mechanistic targets in terms of structural preservation and restoration in patients with CP.

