9.1.2 Secondary Objectives/Outcomes

The models proposed will be tested using general linear models (GLM). We will examine all variables to determine that they are relatively symmetric and unimodal, examine group variances for obvious deviations, and examine the residuals from each model to ensure reasonable adherence to the assumptions of normality and independence. If any variables violate the assumptions, we might transform skewed variables. We will evaluate the comparability of our groups on key demographic variables and will covary variables if necessary (e.g., socioeconomic status). For Efficacy Outcome Measure 1 (refer to section 1.2.1), we will use repeated measures ANOVA or ANCOVA (including intracranial volume as a covariate for macrostructure analyses) with Group (Treatment, Control) as the between-subjects factor and Time of Assessment (baseline, 1 year, and 2 years) and Age as the within-subjects factors. We

will examine the Age x Group x Time interaction and two-way interactions for each analysis and will trim non-significant terms from each model. If GM and WM volumes or DTI metrics vary across time, we will complete trend analysis to identify whether a linear or quadratic function best fits the data. Dependent variables will be evaluated in separate analyses. Dependent variables will be 1) the volume of whole brain gray matter, white matter, and CSF; 2) FA of core white matter pathways (corpus callosum, arcuate/superior longitudinal fasciculus), and 3) MD of gray matter in frontal and temporal cortical regions.

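### The secondary objective asks whether late function improves versus control, but section 9.1.2 specifies no Treatment-versus-Control estimate of function free of imaging covariates, does not say which scan enters the one model that has a Group term, and names an outcome (GOS-EC) that no test list contains

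*Combined protocol and SAP*

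**What the plan says.** The secondary objective in section 1.2 is "To determine if late functional outcomes are improved following the administration of autologous cells compared with subjects in the control group". Two efficacy outcome measures follow. Measure 1 is imaging (volumes and tract metrics) at baseline, 1 year and 2 years. Measure 2 is function (gross motor measures and the psychological batteries): "functional outcomes studies will be performed at baseline, 6 months, 1 year after infusion, and 2 year after infusion".

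Section 9.1.2 treats the two measures differently.

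- **Measure 1** gets a repeated-measures ANOVA or ANCOVA "with Group (Treatment, Control) as the between-subjects factor and Time of Assessment (baseline, 1 year, and 2 years"). The dependent variables are tissue and CSF volumes, FA of named tracts and MD of cortical regions. No functional score is among them.
- **Measure 2** is introduced as a study of brain-behavior relations. Functional scores are correlated with imaging metrics, or are modelled with "individual outcomes as dependent variables with group (Treatment, Control) and MRI/DTI variables as independent variables". Neither the imaging visit nor a baseline functional score is stated for that model.

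Two other places bear on which scan is meant. Section 1.2 says "Specific white matter tract analysis will be identified at baseline MRI and correlated with motor function studies". Section 6.4.9 says "Post-treatment, these same ROIs will be compared to the baseline data, and correlated with any changes in functional outcomes".

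Section 9.1.1 plans repeated-measures models over 6 months, 1 year and 2 years, and survival methods for factors associated with functional improvement. It does not name assignment as a factor or give a contrast on a score. It makes no multiplicity adjustment.

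Section 9.1.2 also assigns GOS-EC as the global outcome, to be correlated with volumes and corpus callosum FA.

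**The concern.** The objective is a between-group comparison of function, so one expects a between-group estimate of function. The only stated functional model with a Group term also holds imaging variables. What its Group coefficient means depends on the scan used, which the plan leaves open.

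At stake is whether the secondary objective has a defined answer before data are seen. Without one, the analyst must choose the score, visit and adjustment later, among many scores, three follow-up visits and no multiplicity adjustment.

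The 6-month visit matters here because it is the only follow-up before the blind is broken (5.1.8 and 5.2.10). It has functional testing but no MRI, so whether it can enter the group-plus-imaging model turns on the same unstated detail.

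**Working it through.** The plan gives no effect size, SD or power for a functional comparison, so there is no figure of its own to reproduce.

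**1. Objective against analysis**

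| Item | Function | Imaging |
|---|---|---|
| Visits | baseline, 6 months, 1 year, 2 years | baseline, 1 year, 2 years |
| Group by Time model in 9.1.2 | none | yes |
| Group effect without imaging covariates | none stated | yes (intracranial volume only, for volumes) |
| Group effect with imaging covariates | yes, imaging visit and baseline score unstated | not applicable |

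**2. What the Group coefficient means**

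Let *a* be the treatment effect on the imaging variable, *b* the effect of imaging on function, and *c* the rest of the treatment effect. In a linear model the total effect is *c + ab*. All values below are assumed; the documents give none.

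- Baseline scan: treatment cannot have changed it, so the Group coefficient estimates the total effect.
- Post-treatment scan, *a* = 0: the coefficient again equals the total effect.
- Post-treatment scan, *a* = 1.0, *b* = 0.5, *c* = 0.5, no measurement error or shared causes: total = 0.5 + 1.0 × 0.5 = 1.0; the coefficient estimates *c* = 0.5.
- The same with MRI reliability 0.7: 0.5 + 0.5 × (1 − 0.7) = 0.65.
- Post-treatment scan, *a* = 1.0, no effect on function at all, and an unmeasured cause with loading 0.5 on both imaging and function: true effect 0, coefficient about −0.25 (simulated).

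The gap can therefore be zero, or can differ in size and direction with unknowns. No single bias figure can be given.

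**3. The 6-month visit**

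Planned follow-up GMFM-88 assessments: 30 children × 3 visits = 90, of which 30 (33%) are at 6 months. If the model needs imaging from the same visit, those 30 cannot enter, and they are all the assessments made before unblinding. If baseline imaging is meant, none is lost for this reason.

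**4. Precision of the missing contrast**

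Section 3 gives 30 children at 2:1, so 20 versus 10 pooled. In units of the outcome SD:

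- Unadjusted 95% CI half-width = t(0.975, 28) × √(1/20 + 1/10) = 2.048 × 0.387 = 0.79.
- Detectable effect, two-sided 0.05, 80% power (assumed), noncentral t: 1.12.
- ANCOVA on baseline, stratum and age (25 error df), before chance covariate imbalance: t(0.975, 25) × √(1 − r²) × 0.387 with t = 2.060. Assumed baseline correlations r = 0.5, 0.7, 0.9 give 0.69, 0.57, 0.35. Simulation with chance imbalance gives 0.71, 0.59, 0.36.
- If only 16 versus 8 are assessed (assumed): 2.074 × 0.433 = 0.90 unadjusted; simulated 0.81, 0.67, 0.41 adjusted.

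These figures describe the analysis to be added. They do not measure harm from leaving it out.

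**5. Named outcomes against listed tests**

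- GOS-EC: in 9.1.2, but not in 6.3 or Appendix B. Appendix A has only a general neuropsychological row, so its silence shows nothing.
- IQ (in the 9.1.2 table) and working memory (only as an example): no dedicated test. Section 6.3.6 calls PPVT-4 an indication of general cognition, but the 9.1.2 table already pairs it with verbal fluency.
- Corticospinal tract: section 1.2 includes it under Measure 1 ("white matter tract such as the corticospinal tract will be measured (fractional anisotropy and mean diffusivity) as well"), but the Measure 1 dependent variables list "FA of core white matter pathways (corpus callosum, arcuate/superior longitudinal fasciculus") and omit it.

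**The case against.** The strongest reply is that the functional comparison is not wholly absent. The brain-behavior model does contain Group. Section 9.1.1 will explore factors associated with functional improvement and promises estimates with 95% intervals for all results; in a randomized trial, assignment is an obvious factor. The study is primarily about safety (9.2), takes imaging as its primary efficacy measure (2.2), and calls its evaluation exploratory. An interval of ±0.79 SD will settle little. The choice of GMFM-88, ANCOVA, covariates and visits is a proposal, and others could be defended.

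Much of this stands and limits the weight. It does not supply the missing contrast: 9.1.1 names neither assignment nor a score and does not define improvement, and the Group term in 9.1.2 answers the objective only under a reading the plan does not state.

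The reply also rules out some stronger readings. A reader might infer that the Group coefficient is necessarily biased. It is not: with a baseline scan, or a post-treatment scan that treatment leaves unchanged, it can equal the total effect. A reader might infer that the 6-month data are excluded, losing a third of the assessments. That follows only if same-visit imaging is required. A reader might infer that the corticospinal tract is not analysed. Section 9.1.2 uses its FA in the outcome table and in the fine-motor example; only the Measure 1 list omits it. Finally, Appendix B is not exhaustive, since it also leaves out CP QOL and the Pediatric Evaluation of Disability Inventory, so the GOS-EC point rests mainly on section 6.3.

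**Conclusion.** The point holds as a gap between objective and analysis. Section 9.1.2 contains no Treatment-versus-Control estimate of a functional score free of imaging covariates, and the one model that could stand in has no stated imaging visit or baseline score. Depending on that visit, its Group coefficient may or may not be the total treatment effect. The documents do not support a claim of a definite bias, or a figure for one. The GOS-EC correlation cannot be run on the tests listed.

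This should be changed, but it does not threaten the trial's primary purpose. The precision figures assume 20 versus 10 with complete data, or the smaller numbers and baseline correlations shown.

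**What to change.** In section 9.1.2:

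1. Add a Treatment-versus-Control ANCOVA of GMFM-88 (listed at every age in Appendix B), adjusted for baseline score, cell-source stratum and age, with no post-treatment imaging covariate. Report the estimate and 95% CI at 6 months (before unblinding) and at 1 year (labelled as after unblinding, using assessments made before any crossover infusion). Present it as an estimate and not a powered test. Report 2-year data descriptively by crossover status.
2. Keep the group-plus-imaging models as exploratory brain-behavior analyses and state their imaging visit.
3. Delete GOS-EC or replace it with a measure that is collected.
4. Minor: tie IQ and working memory to listed tests or delete them, and add corticospinal tract FA and MD to the Measure 1 dependent variables so that they match section 1.2.

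The cost is analysis-plan wording and one model at two visits on data already planned. No new visit, test or participant is needed.
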